4.4.3 VISIT 2, BASELINE & DISPENSE (DAY 0)

Participants who successfully met all eligibility criteria in Visit 1 will directly transition to Visit 2, while continuing to wear the pair of study lenses that has just been fitted.

1. Lens dispense: Participants will be provided with a supply of MiSight CLs to last them for the period of the study.
2. Participant instructions. The participants will be asked to:
 - *Wear the lenses at least 6 days per week and 10 hours per day throughout the study;*
 - *Attend V3 after 2 hours or more of MiSight study lens wear on that day;*

4.4.4 VISIT 3, 2 WEEK FOLLOW-UP

Participant to attend visit after 2 hours or more of MiSight study lens wear.

1. Changes in medical history/medications;
2. Compliance with # of CL wear days/hours per day
3. Presenting VA

5. Spherical over-refraction
6. Slit lamp biomicroscopy
7. Questionnaires (CLIQ, QoV)
8. Lens removal

9. Biomicroscopy examination

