2 OBJECTIVES

The objectives of the study are:

- To measure objective and subjective visual performance, patient satisfaction and to determine if these aspects change over time as myopic young adults adapt to MiSight soft contact lenses.

Primary outcome variable:

- Subjective quality of vision (QoV)

Secondary outcome variable:

- Contact lens Impact on Quality of Life (CLIQ)

[REDACTED]

[REDACTED]

[REDACTED]

[REDACTED]

[REDACTED]

[REDACTED]

[REDACTED]

[REDACTED]

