4.4.2 VISIT 1, SCREENING

A documented informed consent process will be conducted with all participants prior to their enrolment in the study and prior to any data collection or measurements.

Participants will be assigned a study ID number after they sign the consent documentation process i.e. before their eligibility for the study has been confirmed. The investigator will determine participant eligibility using the inclusion and exclusion criteria. Ineligible participants will be discontinued from the study. The procedures to be performed are outlined below:

1. Informed consent
2. Participant demographics and medical history:
 - *Age, Sex*
 - *Medical history/medications, Allergies*
3. CL wear history
 - *Habitual contact lens wear (CL type, cleaning solution (if applicable), wear time)*
4. Subjective questionnaires (QoV and CLIQ) with habitual lenses within the last month of lens wear experience
5. Presenting visual acuity
6. Auto refraction/auto keratometry
7. Sphero-cylindrical refraction, monocular & binocular logMAR distance HIHC VA

13. Slit lamp biomicroscopy
14. MiSight study lens fitting
 - a. The contact lens power will be chosen based on the vertex best sphere refraction.
 - b. The participant will insert the lenses.

- c. Acceptability of lens fit (centration, movement, limbal coverage, overall; YES/NO) will be confirmed.
- d. Monocular over-refraction will be performed to determine if a different power is needed. If any changes are made, the above procedures will be repeated.
- e. The final lens powers for OD and OS and monocular & binocular logMAR distance HIHC VA will be recorded.

15. Confirm eligibility.

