4.4.5 VISIT 4, 1 MONTH FOLLOW-UP

Participant to attend visit after 2 hours or more of MiSight study lens wear.

1. Changes in medical history/medications;
2. Compliance with # of CL wear days/hours per day
3. Presenting VA

[REDACTED]

[REDACTED]

6. Slit lamp biomicroscopy
7. Questionnaires (CLIQ, QoV)
8. Lens removal
9. Biomicroscopy examination
10. Instructions on completing QoV and CLIQ surveys within the V5 time window

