4.4.7 VISIT 6, 3 MONTH FOLLOW UP VISIT AND EXIT

Participant to attend visit after 2 hours or more of MiSight study lens wear.

1. Collect unused study CLs;
2. Changes in medical history/medications;
3. Compliance with # of CL wear days/hours per day

4. Presenting VA

8. Spherical over-refraction

9. Slit lamp biomicroscopy

10. Questionnaires (CLIQ, QoV)

11. Lens removal

12. Biomicroscopy examination

14. Exit visual acuity with habitual correction

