4.5 STUDY PROCEDURES

Table 3 summarizes the procedures at each visit. The order of procedures is described in sections 4.4.2 to 4.4.7.

Table 3: Summary of procedures to be conducted at scheduled visits

Procedures / Data	Screen & BL/Dispensing (75/90mins)	DV++ (30min)	2W (2W from DV) (60mins)	1M (1M from LD) (75mins)	2M (2M from DV) (15mins)	3M (3M from DV)(90mins) Final Visit	Unscheduled/ Adverse Events
Visit window	N/A	≤10 days from BL	± 4 days	+ 5 days - 5 days	+ 7 days - 7days	+ 7 days - 7 days	N/A
Informed consent	✓	-	-	-	-	-	-
Meet inclusion / exclusion criteria	✓	✓	-	-	-	-	-
Demographics	✓	-	-	-	-	-	-
Presenting VA	✓	✓	✓	✓	-	✓	✓
History at baseline	✓	-	-	-	-	-	-
History since last visit, including updated medical problems / previous events / treatment	-	✓	✓	✓	-	✓	✓
Auto-refraction + keratometry	✓	-	-	-	-	-	-
Subjective refraction + VA	✓	-	-	-	-	✓	*
██████████		✓				✓	
██████████	✓	-	✓	✓	-	✓	-
██████████	✓	-	-	-	-	✓	-
██████████	✓	-	-	✓	-	✓	-

	✓	-	-	✓	-	✓	-
Spherical Over-refraction + VA	-	-	✓	-	-	✓	-
Wear time review	-	-	✓	✓	✓	✓	*
Compliance assessment / Lens and solution returns	-	-	✓	✓	-	✓	*
Slit-lamp biomicroscopy: Assessment of lenses worn at visit and ocular assessment	✓	✓	✓	✓	-	✓	✓
Questionnaires (including QOL/OOV questionnaires)	***	+	✓	✓	✓	✓	-
Photos / video	*	*	*	*	-	*	*
Adverse event assessment	✓	✓	✓	✓	-	✓	✓
Visit summary	✓	✓	✓	✓	-	✓	✓
*	At investigators' discretion						
**	If visual acuity (VA) is decreased by 2 lines or more from BL or LD						
***	With habitual lenses						
+	If lenses dispensed						

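### The QoV questionnaire comes before vision testing at baseline but after acuity and slit lamp at Visits 3, 4 and 6: a possible, unquantified bias in comparisons with baseline and Visit 5

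*Combined protocol and SAP*

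**What the plan says.** Section 2 names "Subjective quality of vision (QoV") as the primary outcome and CLIQ as the secondary one. Section 4.5 states: "The order of procedures is described in sections 4.4.2 to 4.4.7". The numbered visit lists are thus a sequence to follow, not just an inventory.

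- **Visit 1 (4.4.2):** "4. Subjective questionnaires (QoV and CLIQ) with habitual lenses within the last month of lens wear experience". The next item is "5. Presenting visual acuity"; refraction (7) and slit lamp (13) come later.
- **Visit 3 (4.4.4):** presenting acuity is item 3, then "5. Spherical over-refraction", slit lamp (6), and "7. Questionnaires (CLIQ, QoV").
- **Visit 4 (4.4.5):** presenting acuity is item 3, then "6. Slit lamp biomicroscopy", with the questionnaires directly after as item 7. Table 3 schedules no over-refraction at 1 month.
- **Visit 5 (4.4.6):** the questionnaires are completed remotely, with no clinical test.
- **Visit 6 (4.4.7):** presenting acuity is item 4, over-refraction 8, slit lamp 9, then "10. Questionnaires (CLIQ, QoV").

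Section 4.5.2 says that the ratings refer to a period of lens wear set by the questionnaire. Section 10.1 compares QoV and CLIQ between visits by paired tests or ANOVA at the 5% level. It does not mention questionnaire position.

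**The concern.** QoV is self-reported in an open-label, single-group trial. Just before rating MiSight vision in the office, participants have read an acuity chart through the lenses and had a slit-lamp examination. At Visits 3 and 6 they have also seen through over-refraction lenses. None of this precedes the baseline or 2-month rating. If these experiences colour the answers, part of a difference between an in-office MiSight visit and baseline reflects when in the visit the form was filled in and not the lens. The same applies to a difference between an in-office visit and Visit 5. There is no control group in which a shift of this kind would cancel, and the analysis in 10.1 has no means of removing it.

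**Working it through.** **1. Position of the questionnaires, from 4.4.2 to 4.4.7 and Table 3**

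| Visit | Lenses rated | Item no. | Acuity before? | Slit lamp before? | Over-refraction before? |
|---|---|---|---|---|---|
| 1 (baseline) | habitual | 4 | no | no | no |
| 3 | MiSight | 7 | yes (3) | yes (6) | yes (5) |
| 4 (1 month) | MiSight | 7 | yes (3) | yes (6) | none scheduled |
| 5 (2 months, remote) | MiSight | – | no | no | no |
| 6 (3 months) | MiSight | 10 | yes (4) | yes (9) | yes (8) |

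Some steps are not visible in the public text (Visit 1 items 8–12, Visit 3 item 4, Visit 4 items 4–5, Visit 6 items 5–7). They do not alter the positions above.

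**2. Which comparisons are exposed**

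- Visit 3, 4 or 6 against baseline: position changes together with lens type.
- Visit 3, 4 or 6 against Visit 5: same lens, but prior testing is present at one visit and absent at the other.
- Visits 3, 4 and 6 among themselves: the same place, after acuity and slit lamp and just before lens removal. Only over-refraction differs, at Visit 4.
- Baseline against Visit 5: no testing precedes either rating.

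**3. The plan's own sample size (4.2.1)**

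Inputs: one group, m = 3 measurements (baseline, 1 month, 2 months), f = 0.25, power 0.95, alpha 0.05. The plan states neither the correlation nor a sphericity correction; I assume rho = 0.5 and epsilon = 1.

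lambda = f² × n × m / (1 − rho) = 0.0625 × 43 × 3 / 0.5 = 16.125, with 2 and 84 degrees of freedom. Power is 0.951, and 43 is the smallest n that reaches 0.95. The stated figure reproduces. Dropout: 43/0.90 = 47.8 (48) and 43/0.85 = 50.6 (51), so 50 is reasonable. Questionnaire order changes none of this. In the powered set only the 1-month visit has testing before the form, and that visit has no over-refraction.

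**4. Illustration of sensitivity**

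The documents give no order effect, so I assume one: true change zero, n = 43, two-sided 5% paired t-test (sidedness is also assumed), and a shift of d SDs of the paired difference. The noncentrality is d × √43 = 6.557d, with 42 degrees of freedom and critical value 2.018.

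| Assumed shift d | Noncentrality | Probability of a significant result |
|---|---|---|
| 0 | 0 | 0.050 |
| 0.1 | 0.656 | 0.098 |
| 0.2 | 1.311 | 0.249 |
| 0.3 | 1.967 | 0.485 |

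If the shift is instead expressed in SDs of the score, the SD of the difference is √(2(1 − rho)) times the score SD. For rho from 0.3 to 0.7 the probabilities are then 0.08–0.13, 0.19–0.38 and 0.37–0.70 for shifts of 0.1, 0.2 and 0.3.

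For the three-measurement ANOVA with the shift at 1 month only, means (0, b, 0) give f² = 2b²/9. At rho = 0.5 the rejection probabilities are 0.094, 0.246 and 0.502 for b = 0.1, 0.2 and 0.3.

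**The case against.** The strongest reply is that these are recall ratings. Baseline asks about the last month of wear, and 4.5.2 ties every rating to a period of wear. A chart read a few minutes earlier should matter much less to such a rating than to a rating of vision at that moment. Nothing says participants are told their acuity. This stands as a reason to expect a small effect, though the documents do not show that it is zero.

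The objective in section 2 is change during adaptation, and the hypothesis in section 3 concerns good scores with MiSight, not change from habitual lenses. Adaptation comparisons among Visits 3, 4 and 6 are largely protected. This also stands, but the steps from Visit 4 to 5 and from 5 to 6 remain exposed.

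An open-label, single-group contrast with baseline already mixes lens, expectation and time, so equal ordering would not make it clean. That is true, but it does not justify leaving in a further difference that can be removed.

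Finally, the rejection rates follow wholly from the assumed shift; any bias of that size, from any cause, would give the same figures. This is correct, so they are offered only as an illustration, with zero in the range.

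A reader might infer that every between-visit comparison in 10.1 is confounded, or that over-refraction precedes all in-office ratings. The table of positions rules out both.

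**Conclusion.** The point holds in a limited form. The ordering difference is plain from the visit lists and does not depend on any hidden step. It is a possible source of bias in comparisons of Visit 3, 4 or 6 with baseline or with Visit 5, including the 1-month point among the three powered time points.

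A reader might go further and conclude that QoV changes in this trial are biased, or that the false-positive rate is about 48%. The documents support neither: they give no size and no direction for an order effect. The range of 5% to about 48% rests on an assumed shift of 0 to 0.3 SD of the paired difference, no true change, 43 completers and a two-sided paired t-test, where 10.1 also allows Wilcoxon or ANOVA. The sample size is not affected. The case for acting is that the ambiguity touches the primary outcome and can be removed at almost no cost.

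**What to change.** In 4.4.4, 4.4.5 and 4.4.7, move the CLIQ and QoV questionnaires to directly after the medical-history and wear-time items and before presenting acuity. Participants already attend these visits after at least 2 hours of study-lens wear, and lens removal comes later in each list, so the lenses are still in place. The order then matches Visits 1 and 5.

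The cost is the reordering of three lists and the matching CRF pages. No visit time, procedure or participant is added. The sponsor should check that no step withheld from the public text requires the present order.

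If data have already been collected, report the difference in questionnaire position as a limitation of the comparisons with baseline and with Visit 5.

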4.4.5 VISIT 4, 1 MONTH FOLLOW-UP

Participant to attend visit after 2 hours or more of MiSight study lens wear.

1. Changes in medical history/medications;
2. Compliance with # of CL wear days/hours per day
3. Presenting VA

[REDACTED]

[REDACTED]

6. Slit lamp biomicroscopy
7. Questionnaires (CLIQ, QoV)
8. Lens removal
9. Biomicroscopy examination
10. Instructions on completing QoV and CLIQ surveys within the V5 time window

4.4.6 VISIT 5, 2 MONTH FOLLOW-UP

This visit will be conducted remotely to reduce the number of study visits.

Participants will be sent a link to an electronic questionnaire which will include version questions to confirm their contact lens wearing time (i.e. typical hours per day and days per week) plus the QoV and CLIQ surveys. If electronic access is not available or fails then the questions can be emailed or provided in paper form.

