4.5.1 CASE HISTORY

Demographics:

Demographic information from the participant will be obtained, including age and sex.

Medical History:

At screening, information will be obtained from participants about the current medication, allergies, and any medical conditions. At visits 2 (if applicable), 3, 4 and 6 participants will be asked about changes in their medication or health.

Contact Lens History:

Information will be obtained from the participant about the current contact lens type (lens name, brand), lens power and use of artificial tears. Participants will be asked their typical lens wear time (hours/day and days/week).

4.5.2 QUALITY OF LIFE (CLIQ) AND QUALITY OF VISION QUESTIONNAIRES (QOV):

Participants will be asked to complete questionnaires based on the time period of contact lens wear specified in the questionnaire.

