7.3 REPORTING ADVERSE EVENTS

All potential Serious and Unanticipated Adverse Device Effects that are related or possibly related to participant's participation will be reported to the Principal Investigator and the sponsor within 24 hours of the investigator becoming aware of the event. The Investigator will report the event to the University of Waterloo's Office of Research Ethics (ORE) within 24 hours of becoming aware, as

per their requirements (by fax, mail/delivery, phone, or email). All fatal or life threatening events will be reported immediately to the ORE.

Significant and Non-Significant Adverse Events will be reported to the sponsor as soon as possible, but no later than 5 working days after the occurrence. The Investigator will report the event to the ORE as per ORE requirements (by fax, mail/delivery, phone, or email).

Details of all adverse events will be included in the study report.

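### The 2-month remote contact asks nothing about adverse events or health changes, so Visits 4 and 6 leave 56 planned days without a scheduled query; separately, the 5-working-day reporting limit lacks a workable starting point

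*Combined protocol and SAP*

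**What the plan says.** Section 4.4.6 describes Visit 5 as a remote contact, made remote to reduce the number of study visits. The electronic form contains "questions to confirm their contact lens wearing time", put in terms of typical daily hours and weekly days, together with the QoV and CLIQ surveys. No health, medication or event item is listed.

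Table 3 (Section 4.5) agrees. The row "Adverse event assessment" is ticked at screening/baseline, the separate dispensing visit, 2W, 1M, 3M and unscheduled visits, and carries a dash at 2M. The row "History since last visit, including updated medical problems / previous events / treatment" also has a dash at 2M, and is ticked at every other column after baseline. Wear time review is ticked at 2M.

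Section 4.5.1 gives the same picture in words: "At visits 2 (if applicable), 3, 4 and 6 participants will be asked about changes in their medication or health".

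On reporting, Section 7.3 requires significant and non-significant events to reach the sponsor "as soon as possible, but no later than 5 working days after the occurrence". For serious and unanticipated device effects the limit is "within 24 hours of the investigator becoming aware of the event". Table 5 repeats the 5 working days for the first group but does not say when they begin.

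**The concern.** Visit 5 is the only scheduled contact after dispensing at which nobody asks whether anything has gone wrong with the eyes. All three places agree, so this is how the schedule was written; it is not a blacked-out row or a broken table.

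Three things are at stake.

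- **Ascertainment.** Section 7.3 promises details of all adverse events in the study report. Between Visits 4 and 6 a mild event that resolves reaches the record only if the participant volunteers it or recalls it at Visit 6.
- **Reading the Visit 5 scores.** QoV is the primary outcome, and Section 4.2.1 sizes the study on baseline, 1 month and 2 months, so Visit 5 supplies one of those three measurements. The form asks for typical hours and days of wear, and an answer about typical wear can pass over a short interruption. Medication is not asked about at all, although Section 8 links continued participation to topical ocular medication and how long it is used.
- **The reporting clock.** This is a separate matter. A limit counted from occurrence runs whether or not anyone at the site knows of the event. Some listed events, such as asymptomatic corneal infiltrates (code 23), may have no knowable date of occurrence when first seen at the slit lamp.

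**Working it through.** The plan states no figure for the interval between event queries, so there is none to reproduce. The inputs are the visit days and windows.

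**Inputs**
- Visit 4: day 28 ± 7 (Table 2); Table 3 gives ± 5 for the same visit.
- Visit 5: day 56 ± 7 (Tables 2 and 3).
- Visit 6: day 84 ± 7 (Tables 2 and 3).

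**Gap between scheduled queries as the plan stands (Visit 4 to Visit 6)**
- Planned: 84 − 28 = 56 days, or 8 weeks. As a share of the 84-day wear period, 56/84 = 67%.
- Shortest, Table 2 windows: (84 − 7) − (28 + 7) = 77 − 35 = 42 days, or 6 weeks.
- Longest, Table 2 windows: (84 + 7) − (28 − 7) = 91 − 21 = 70 days, or 10 weeks.
- With Table 3's ± 5 for Visit 4: 77 − 33 = 44 days to 91 − 23 = 68 days.

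**Gap if Visit 5 carried an event item**
- Planned: 56 − 28 = 28 days, then 84 − 56 = 28 days.
- Visit 4 to Visit 5: 49 − 35 = 14 to 63 − 21 = 42 days (16 to 40 with ± 5 for Visit 4).
- Visit 5 to Visit 6: 77 − 63 = 14 to 91 − 49 = 42 days.

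The planned gap is halved, and the longest allowed gap falls from 70 to 42 days.

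**The reporting clock, taken on its own**

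Assume that 5 working days is about 7 calendar days, that onset is uniform over 84 days of wear, and that each event is first learned of at the next scheduled query. These are illustrations; the documents give no event rates or onset times. An event is then on time only if it began in the last 7 days before a query.
- Visit 4 to Visit 6 today: (56 − 7)/56 = 49/56 = 88% already overdue when first learned of.
- The same period with a Visit 5 item: (28 − 7)/28 = 21/28 = 75% overdue.
- Whole study today, queries at days 14, 28 and 84: (84 − 3 × 7)/84 = 63/84 = 75% overdue.
- Whole study with a Visit 5 item, queries at days 14, 28, 56 and 84: (84 − 4 × 7)/84 = 56/84 = 67% overdue.

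Day 14 for Visit 3 is taken from Table 2. Section 4.1.1 says day 7, but the whole-study shares are the same with either day, because every gap is at least 7 days long.

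**The case against.** The case for leaving Visit 5 alone has weight. Participants are established soft lens wearers using an approved daily disposable lens, and Section 6 describes the study as minimal risk. A participant or the investigator can ask for an unscheduled visit at any time (Section 4.4.9). Visit 6 asks about changes in medical history and medication, and examines the eye before and after lens removal. Section 7.1 already keeps many transient symptoms out of adverse event reporting. Event rates are neither the primary outcome nor the named secondary outcome. All of this stands, and it limits the point to an inexpensive improvement. It does not supply a scheduled query, and one more item on an existing form adds no visit, so the stated reason for making Visit 5 remote is not disturbed.

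Four stronger readings are tempting, and the documents do not support them.

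- *That events will be under-counted and misdated.* No rate is given from which to show this. A risk of late detection and imprecise recall, mainly for mild or resolved events, is as far as the text goes.
- *That a QoV score given during an interruption of wear cannot be recognised.* Visit 5 does ask hours per day and days per week, so a current or long interruption should show. Only a short one could be masked.
- *That any break in wear is a missed adverse event.* Codes 17 and 24 are narrower: code 17 needs therapeutic treatment or a sign or symptom that forces at least 2 weeks without lenses, and code 24 a recommendation to stop for more than 1 day. The plan requires wear on only 6 days a week, so a weekly day off is permitted.
- *That the Visit 5 omission causes the reporting-clock problem.* An event just after Visit 3 that is first mentioned at Visit 4, some 14 days later, is overdue too, and a Visit 5 item leaves planned gaps of 28 days. Section 7 also refers to a site procedure (SOP012), not reproduced in the documents, which may say more about reporting.

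**Conclusion.** The point holds. No adverse event or medication query is scheduled between Visit 4 and Visit 6: 56 days as planned, 42 to 70 days within the Table 2 windows, or 44 to 68 days with Table 3's window for Visit 4. These figures rest only on the stated visit days and windows. A reader might take 8 weeks as the minimum, but it is the planned value; the windows allow 6 to 10 weeks. The effect on the data is modest and cannot be quantified from the documents.

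The clock is a separate drafting inconsistency. Section 7.3 counts from occurrence for significant and non-significant events and from awareness for serious and unanticipated ones, and Table 5 is silent. Under the uniform-onset illustration, the occurrence-based limit is missed for about two-thirds to three-quarters of events that surface only at a scheduled query, so changing Visit 5 alone would not cure it.

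**What to change.** **Visit 5.** Add one item to the form asking whether, since the last visit, the participant has had an eye problem, sought eye care, used eye medication, or stopped lens wear because of an eye problem or on professional advice. Word the last part so that the permitted weekly day off is not flagged and so that it matches code 24's threshold of more than 1 day. Tick the 2M cells in Table 3 for adverse event assessment and history, and add Visit 5 to the list in Section 4.5.1. State who reads the replies and how soon, with the existing unscheduled-visit process used where the investigator judges it necessary.

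**Reporting limit.** Reconcile Section 7.3 and Table 5 on one starting point that can be met in practice. Investigator awareness is an obvious candidate, since the 24-hour rule in the same section already uses it. Check the result against SOP012.

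**Visit 4 window.** While Table 3 is open, reconcile its ± 5 days with the ± 7 days in Table 2.

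**Cost.** One question on an existing form, edits to two tables and two sections, prompt review of replies, and possibly some extra unscheduled visits. No scheduled visit is added.
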